We will perform a retrospective cohort study to compare VTE risk and VTE risk factors in adults with IBD, RA, and PsA and matched controls between January 1, 1998 and January 1, 2018, within the RCGP RSC network. In the cohorts with and without inflammatory conditions we will estimate the risk of VTE overall, and for PE and DVT separately, using unadjusted Cox proportional hazards models, stratified by matched set (exposed cohort versus unexposed cohort), to provide overall hazard ratios for the association with each outcome. Models will be subsequently adjusted for sociodemographic and clinical and VTE risk factors in multivariable analysis to explore potentially important associations with VTE. We will then repeat the same analyses for each autoimmune condition separately. We will perform prespecified sensitivity analyses to explore the robustness of any potential associations.

Lay summary

Blood clots occurring in the legs and in the lungs are relatively common; they occur in around 3 in a 1000 people per year. They can cause disability and are also potentially life threatening. When a clot occurs in the legs it is called a deep vein thrombosis or DVT. When they occur in the lungs they are called a pulmonary embolism or PE. The risk for DVT and PE is higher in people with conditions which cause inflammation. The most common of these are inflammatory bowel disease (ulcerative colitis and Crohn's disease), rheumatoid arthritis, and psoriatic arthritis (a condition comprised of psoriasis and joint inflammation).

What is not known is how much higher the risk of DVT and PE is in these groups compared with people without inflammatory disease, and what causes the excess risk in these people. This study aims to assess the measure the exact increase in risk for DVT and PE in people with these inflammatory conditions and to identify which risk factors are most strongly associated with the increased risk. These data should help us understand the causes of blood clot risk in these inflammatory conditions and identify targets for reducing risk.

Introduction

Venous thromboembolism (VTE), comprising pulmonary embolism (PE) and deep vein thrombosis (DVT), is relatively common, with an incidence in the general population of around 3 cases per 1000 patient years.¹ It is associated with significant morbidity and mortality.

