The RCGP RSC database contains information on clinical diagnoses, anthropometric measurements (e.g., body mass index; BMI), laboratory tests results, and prescriptions, coded with the Read coding system (a thesaurus of clinical terms).¹¹ UK general practice lends itself to this type of study because it is a registration-based system (each patient can only be registered with a single GP), it has been computerised since the 1990s, and pay-for-performance targets introduced in 2004 have resulted in consistent high-quality clinical data entry about chronic disease.¹² All RCGP RSC registered practices have electronic laboratory links; meaning all test results are automatically coded and uploaded to the GP computer system. Studies using RCGP RSC data have been published across a range of chronic diseases.¹³⁻¹⁵

Study population

Adult patients (aged ≥18) contributing to RCGP RCS primary care database between January 1, 1998 and January 1, 2018, will be eligible for inclusion.

Definition of the exposed cohort with systemic inflammatory disease

The exposed cohort will include all individuals with an existing or incident diagnosis of IBD, RA or PsA (systemic inflammatory diseases) in the RCGP RCS over the study period. IBD, RA or PsA will be identified using Read diagnostic codes previously validated in UK primary care studies.¹⁶⁻¹⁸ Follow-up for exposed individuals will begin on the latest of the date of diagnosis indicated by first diagnostic code, January 1 1998 or 180 days after practice registration.

Definition of the matched unexposed cohort

The matched unexposed cohort will be defined by matching individuals in the exposed cohort with individuals who were never diagnosed with a systemic inflammatory disease either prior to or during the study period by age and sex at GP practice level. Unexposed individuals will require at least one year of follow-up when matched to minimise the risk they had a nonrecorded existing diagnosis of a systemic inflammatory disease of interest. Follow-up for each matched individual will begin at the start of follow-up of their exposed counterpart.

Follow-up will end at the earliest of the study end-date (January 1, 2018), the date of patient transfer from an included practice, date of death, or the date an individual developed an outcome of interest.

Outcomes

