The pre-specified outcomes include the time to incident VTE (either PE or DVT), time to PE, and time to DVT. These outcomes will be defined using Read codes that have been previously validated in a similar UK primary care database.¹⁹ Time to each outcome will be compared between individuals with a systemic inflammatory disorder and the matched control population, and across IBD, RA and PsA subgroups.

Baseline characteristics and VTE risk factors

Baseline measures will comprise sociodemographic characteristics, clinical features and biomarkers, selected based on clinical expertise and existing literature demonstrating an established association with VTE or evidence to support an association with VTE among individuals with systemic inflammatory disorders.^{4, 7} Socioeconomic status will be defined using the official national measure; the index of multiple deprivation (IMD).²⁰ This will be calculated at the point of data extraction, using patient postcode, with the resultant scores stratified by deprivation quintile. Ethnicity will be extracted from the primary care record and grouped into the major UK ethnic groups; white, black, Asian, mixed, and others.²¹ BMI will be defined as the most recently recorded measurement prior to the study start date. Smoking status and alcohol use will be defined using the most recently recorded data prior to the study start date. Diagnostic codes will be used to define the presence of comorbidities at baseline: hypertension, hyperlipidaemia, diabetes, peripheral vascular disease, cardiovascular disease (Atrial fibrillation, angina, myocardial infarction, congestive heart failure), cerebrovascular disease, cancer, chronic obstructive pulmonary disease, chronic kidney disease (stages 3–5), liver disease, recent hospitalisation, joint replacement, and fractures. Diabetes and diabetes type will be identified using an algorithm developed for use within the RCGP RSC database.²²

The Read codes used to describe cardiovascular disease within the RCGP RSC database have been previously reported.^{23, 24} We will also extract records of pregnancy and reduced mobility. Biomarkers and laboratory tests including cholesterol and blood pressure will be derived by taking the most recent value in the year before cohort entry.

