We will examine the following medications commonly used for the management of systemic inflammatory disorders: non-steroidal anti-inflammatory drugs (NSAIDs), oral corticosteroids, disease modifying anti-rheumatic drugs (DMARDs), other non-biologic immunosuppressant medications, and biologic therapies (where recorded). We will also include hormone therapy (hormonal contraceptives, hormone replacement therapy). We will also extract information on prescribing of antiplatelet agents (aspirin or adenosine diphosphate receptor inhibitors) and lipid lowering therapy (statins, fibrates, or ezetimibe). Prescribing at the study start date will be defined as the presence of an issued prescription in the three months preceding or one month after the date of diagnosis.

Statistical Analyses

We will describe the characteristics at baseline for individuals with IBD, RA and PsA separately in comparison to the matched unexposed cohort. We will evaluate differences in characteristics at entry between those with and without systemic inflammatory disease using the χ^2 test for categorical variables and the unpaired t-test for continuous data. All reported *P*-values will be two-sided.

Event rates for the primary and secondary outcomes will be compared in individuals with and without systemic inflammatory disease, calculated as the number of events divided by the total person-years of follow-up, and expressed as the number per 1000 person-years.

Risk of VTE

We will estimate the risk of VTE overall, and for PE and DVT separately, using unadjusted Cox proportional hazards models, stratified by matched set (exposed cohort versus unexposed cohort), to provide overall hazard ratios for the association with each outcome. Models will be subsequently adjusted for sociodemographic and clinical and VTE risk factors in

multivariable analysis. We will then repeat the same analyses for each autoimmune condition separately.

Predictors of VTE

Subsequently, we will run multivariable Cox models to examine the relative influence of individual VTE risk factors in the cohort with systemic inflammatory disease and control cohort. We will then explore the impact of changing platelet count over the study follow-up on VTE risk by including platelet count as a time varying exposure in survival models.

Sensitivity analysis

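### VTE event rates are crude while age and sex are matched only at entry, so the absolute comparison may under- or overstate the excess, and crude rates cannot rank the diseases

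*Combined protocol and SAP*

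**What the plan says.** Under Statistical Analyses: "Event rates for the primary and secondary outcomes will be compared in individuals with and without systemic inflammatory disease", and the rate is "calculated as the number of events divided by the total person-years of follow-up, and expressed as the number per 1000 person-years". The section mentions no standardisation, no split by attained age and no confidence interval for the rates. They are the only absolute measure in the plan; the other effect estimates are Cox hazard ratios, first stratified by matched set and then adjusted.

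Under Definition of the matched unexposed cohort, controls are matched "by age and sex at GP practice level". Their clock is aligned at the start: "Follow-up for each matched individual will begin at the start of follow-up of their exposed counterpart". It is not aligned at the end: "Follow-up will end at the earliest of the study end-date (January 1, 2018), the date of patient transfer from an included practice, date of death". An outcome event also ends it. A control is not censored when the exposed counterpart leaves. The study window runs "between January 1, 1998 and January 1, 2018", so one person can contribute up to 20 years.

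Two stated aims bear on how the rates will be read. The Lay summary says "What is not known is how much higher the risk of DVT and PE is in these groups compared with people without inflammatory disease". The Outcomes section says that time to each outcome will also be compared "across IBD, RA and PsA subgroups", and gives no method for that comparison.

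**The concern.** Matching with a shared start date makes the cohorts alike in age and sex on day one. It does not keep their person-time alike. If exposed people die sooner, their later and older person-years are missing from the denominator while the controls' remain. If one cohort leaves its practices faster, or at different ages, the same drift occurs in one direction or the other. A total-person-years rate averages over whatever age mix results.

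At stake is any statement of excess VTE per 1000 person-years, because it can come only from these rates. A published crude rate ratio could also differ visibly from the hazard ratio, with nothing in the plan to explain why.

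The comparison across diseases is exposed in a simpler way. Each disease is matched to its own controls, and the diseases are not matched to each other. Crude rates for IBD, RA and PsA therefore mix disease effect with the age and sex of the people who have each disease.

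**Working it through.** The plan gives no expected rate ratio, event count, mortality, transfer rate or age gradient for VTE, so it has no figure to reproduce. Every input below except the 20-year window is an assumption.

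**Model.** Annual cohort model with identical entry ages in both cohorts: ages 18–84, weight exp(−((a−55)/18)²).
- VTE hazard: 0.00025·exp(0.05(age−20)), multiplied by 1.5 if exposed. The gradient is exp(0.5) = 1.65 per decade.
- Mortality: 0.0003·exp(0.085(age−20)), multiplied by 1, 1.5 or 2 if exposed.
- Transfer: 10% a year under 45 and 3% a year from 45, the same in both cohorts.

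**Formula.** Let R be the crude ratio and r the exposed crude rate. The crude excess is r(1−1/R). On exposed person-time the true excess is r(1−1/1.5) = r/3. The share of the true excess recovered is therefore 3(1−1/R).

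| Entry | Exposed mortality ratio | R | 3(1−1/R) | Excess too low by |
|---|---|---|---|---|
| All followed for up to 20 years | 1 | 1.493 | 0.991 | 1% |
| Same | 1.5 | 1.433 | 0.907 | 9% |
| Same | 2 | 1.385 | 0.834 | 16–17% |
| Uniform entry 1998–2018 | 1.5 | 1.455 | 0.938 | 6% |
| Same | 2 | 1.42 | 0.887 | 11% |

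In the third row, R = 1.385 gives 16.6%. A slightly different handling of events within the year gives R = 1.390 and 15.8%; I quote about 16%.

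In rates, the second row is 3.53 v 2.46 per 1000, a crude excess of 1.07. On exposed person-time the true excess is 3.53/3 = 1.18, so the crude figure is 9% low. On control person-time it would be 2.46 × 0.5 = 1.23, and the crude figure 13% low (23% for mortality ratio 2). The percentage depends on the standard; I use exposed person-time because the fix below does.

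**Unequal transfer, all followed for up to 20 years.**
- Controls aged 45 and over leave at 5% a year rather than 3%: R = 1.48 with mortality ratio 1.5, 1.51 with 1.25, and 1.55 with equal mortality.
- The same controls leave at 6%: R = 1.51 with mortality ratio 1.5.
- Controls under 45 leave at 12% against 7% or 6% for the exposed: R = 1.401 (mortality ratio 1.5) and 1.346 (mortality ratio 2).

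The sign depends on who leaves and at what age.

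**A second set of assumptions.** VTE hazard of 3 per 1000 at age 55, rising by a factor of 1, 1.5 or 2 per decade; mortality 0.5% a year at 55; mean entry age 45 or 60; true ratio 1.5.
- Flat risk with age: R = 1.50 throughout.
- Rising risk, equal mortality and transfer: 1.47–1.50.
- Rising risk, exposed mortality 1.5–2 times higher, equal transfer: 1.29–1.47.
- Rising risk, equal mortality, transfer 2% a year exposed v 8% controls: 1.53–1.61.

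In simulated matched sets with four controls each, the crude ratio was 1.32–1.48 while the Cox model stratified by set gave 1.48–1.51.

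**Across diseases.** Three diseases have the same true ratio of 1.5, mortality ratio 1.5, equal transfer, and mean entry ages 40, 50 and 60. Exposed crude rates per 1000 are 3.76, 5.10 and 6.91 (factor 1.5 per decade) or 3.92, 6.53 and 10.68 (factor 2). The spread is 6.91/3.76 = 1.8-fold to 10.68/3.92 = 2.7-fold, from age alone.

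**Does the fix work?** In the first model, direct standardisation to exposed person-time in 5-year attained-age bands returns a ratio of about 1.50 in every scenario; 10-year bands return 1.49–1.50.

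**The case against.** The strongest reply is that the study's effect measure is the hazard ratio from Cox models stratified by matched set. These compare people at the same time since a shared start, hence at about the same attained age. The rates are conventional descriptive context, and some difference from the hazard ratio is ordinary. That stands: the main results are not biased by this route.

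A reader might infer that the crude comparison is bound to understate the excess. The documents do not support that. It needs VTE risk that rises with age, and exposed person-time that ends up younger through higher mortality or through differences in transfer. The plan gives no figure for any of these, and plausible transfer patterns remove or reverse the bias.

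A reader might also infer that the plan intends to rank IBD, RA and PsA by crude rate. It does not say so: the rates are specified for people with and without disease, and the comparison across diseases concerns time to outcome. But that comparison has no stated method, and the Objective in the Abstract asks for VTE risk by disease type, so the crude rates are the figures nearest to hand.

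Finally, the Lay summary's question can be read as relative, which the hazard ratios answer, and no rate difference is planned. That is fair. Still, the plan does say that the rates will be compared, and readers will subtract them.

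**Conclusion.** The point holds for the absolute rates and for any excess or between-disease reading taken from them, and no further. The crude comparison may under- or overstate the excess. With a true ratio of 1.5, a VTE gradient of 1.65 per decade, equal transfer and exposed mortality 1.5 to 2 times higher, the crude ratio is about 1.39 to 1.46 and the excess about 6% to 16% low on exposed person-time. A steeper gradient enlarges this. A flat gradient removes it, similar follow-up leaves almost none, and more transfer among older controls can reverse it. All of these inputs are assumptions. The set-stratified hazard ratios are sound on this point. Crude rates by disease should not serve the comparison across IBD, RA and PsA.

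**What to change.** In Statistical Analyses, add that follow-up will be split by attained-age band (for example 5 years) and sex. Report directly standardised rates on one common standard, such as pooled exposed person-time, for the exposed cohort, the unexposed cohort, and each disease with its matched controls. Give the standardised rate difference per 1000 person-years with its 95% CI as the absolute measure, and label crude rates as descriptive. Showing length of follow-up and reasons for its ending by cohort would let readers see which way the crude rates lean.

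The cost is a sentence or two of protocol text and a small amount of programming. The dates, ages and sex are already needed for matching and follow-up, so no new data are required.

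### No lag or value-assignment rule is given for the time-dependent platelet count, so tests prompted by a not-yet-coded VTE could produce a reverse-causation hazard ratio

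*Combined protocol and SAP*

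**What the plan says.** The combined protocol and SAP covers this analysis in one sentence under Statistical Analyses, Predictors of VTE. The aim is to "explore the impact of changing platelet count over the study follow-up on VTE risk", and the method is "including platelet count as a time varying exposure in survival models". The preceding sentence says "we will run multivariable Cox models to examine the relative influence of individual VTE risk factors", so a Cox model is the natural reading, although the platelet sentence does not name one.

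Four other places bear on timing:

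- Data source: practices have electronic laboratory links, "meaning all test results are automatically coded and uploaded to the GP computer system". No filter on the reason for a test is mentioned.
- Outcomes: "These outcomes will be defined using Read codes that have been previously validated in a similar UK primary care database". No rule separates symptom onset or work-up from the coded date.
- Definition of the matched unexposed cohort, final paragraph: one of the events that ends follow-up is "or the date an individual developed an outcome of interest". No window before it is excluded.
- Baseline characteristics and VTE risk factors: laboratory values "will be derived by taking the most recent value in the year before cohort entry". This rule governs baseline only.

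The one sensitivity analysis described moves the start of follow-up to 2004 and does not concern test timing.

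**The concern.** At each event time, a Cox model with a time-dependent covariate compares the case's current value with the current values of everyone still at risk. If current means the latest recorded value, some cases may contribute a blood count taken because they already had symptoms of the clot. Others at risk at that moment have no such reason to have been tested. If the work-up values differ systematically from routine ones, the model attributes to platelets a difference that the event itself produced.

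Covariate adjustment would not remove this, and a larger cohort would only make a false estimate more precise. The Lay summary hopes that the data will point to ways of lowering clot risk. A spurious platelet association, in either direction, could be taken up in that spirit.

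**Working it through.** **Figure to reproduce.** There is none. The documents give no event count, platelet distribution, effect size or testing frequency. The check is therefore a reading of the plan plus an illustration whose inputs are assumptions.

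**Reading.** With results loaded automatically, a Read-coded outcome, follow-up to the outcome date and no lag, nothing stated keeps a work-up test dated before the coded event from serving as the exposure.

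**Assumed inputs.**

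- The true HR is 1.00, and routine platelet values have SD 1.
- A share f of cases has a work-up test 0 to 14 days before the coded date, with its mean shifted by s SD.
- There are 1500 cases, each with 10 risk-set controls (a sampled version of the Cox partial likelihood), and 300 replicates.
- Tests are two-sided, as the plan says. The 0.05 level is assumed, because the plan states none.

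**Closed form.** To first order, the case mean exceeds the risk-set mean by f × s. Dividing by the variance of 1 gives log HR per SD ≈ f × s.

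- f = 0.10, s = 0.25: 0.025, HR exp(0.025) ≈ 1.03
- f = 0.25, s = 1: 0.25, HR exp(0.25) = 1.28
- f = 0.50, s = 1: 0.50, HR exp(0.50) = 1.65
- f = 0.50, s = −0.5: −0.25, HR exp(−0.25) = 0.78

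**Simulation without a lag.** HR per SD, with the share of replicates significant at 0.05 in brackets:

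| Share f | s = −0.5 | s = 0 | s = 0.25 | s = 0.5 | s = 1 |
|---|---|---|---|---|---|
| 10% | 0.95 (43%) | 1.00 (5%) | 1.02 (16%) | 1.05 (45%) | 1.11 (96%) |
| 25% | 0.88 (99%) | 1.00 (3%) | 1.07 (64%) | 1.13 (100%) | 1.28 (100%) |
| 50% | 0.78 (100%) | 1.00 (7%) | 1.14 (100%) | 1.28 (100%) | 1.62 (100%) |

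The closed form and the simulation agree closely; the largest gap is 1.65 against 1.62. The rejection rates depend on the assumed 1500 cases, so the HRs are the more useful columns.

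**Simulation with a 30-day lag.** The HR is 1.00 in every scenario, with rejection in 3% to 7% of replicates. The Monte Carlo standard error at 5% is √(0.05 × 0.95 / 300) ≈ 1.3 percentage points, so this is consistent with the nominal level. The result holds by construction, because 30 days exceeds the assumed 14-day window. It shows that a sufficient lag removes the bias, not that 30 days is sufficient in these data. If a fraction q of the work-up tests is older than the lag, the remaining bias in log HR is about q × f × s.

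**The case against.** The strongest reply is that this is an under-specified sentence, not a wrong decision. A reader might infer that the plan fixes the lag at zero and so builds reverse causation into its model. It does not: it gives no value-assignment rule, lagged or unlagged. That stands, and the point is limited to what the usual implementation would do.

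A reader might also infer that a test dated on the day of the coded event drives the estimate. Under standard (start, stop] counting-process coding, a value dated that day applies only afterwards and the event takes the previous value. Only tests dated before the coded date matter, and f should be read that way.

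The mechanism is partly inferred. The documents do not say how often a platelet count precedes a coded VTE, or whether results from hospital work-up reach the GP record with an earlier date. People still at risk may also be tested when unwell, for instance during active inflammatory disease, which would narrow the contrast. This stands, and it is why the bias is called possible. At s = 0 there is none.

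Importance is limited too. The platelet analysis is described as exploratory, platelets are not named in the objectives, and the Lay summary's hope concerns the study as a whole. This bears on the weight of the point, but an exploratory label does not make a reverse-causation HR interpretable.

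Finally, the baseline laboratory rule might be read as part of the defect. It is not: it uses values from before cohort entry, so its time order is correct.

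**Conclusion.** The point holds as a gap that is worth closing and cheap to close. Carried out in the ordinary way, the planned analysis can let pre-coding work-up tests act as the exposure, and nothing in the plan prevents it.

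The size and direction of any bias are unknown. With a true HR of 1.00, the illustration runs from no bias (no shift), through 1.02 per SD (10% of events, 0.25 SD), to 1.28 (25%, 1 SD) and 1.62 (50%, 1 SD). A downward shift of 0.5 SD gives 0.95 to 0.78. These values rest wholly on the assumed f and s and are not predictions for this cohort.

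A reader might extend the point to the study's main findings. The documents do not support that: the exposed-versus-unexposed hazard ratios for VTE, PE and DVT do not use follow-up platelet values. Only the platelet analysis is affected.

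**What to change.** Add to Predictors of VTE a rule along these lines:

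- At each event time, use the last platelet count recorded at least a pre-specified interval earlier, for example 30 days.
- Repeat with another interval, for example 90 days, as a sensitivity analysis.
- Report the unlagged model only as a contrast.
- If a maximum carry-forward is set, state how person-time without a valid value is handled (for example a missing category, or censoring of that person-time), and compare its amount between the two cohorts.

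The intervals are examples; the documents offer no basis for a particular length, which is why more than one should be run. The rule belongs in the protocol that the Scientific rigor and study registration section undertakes to make public ahead of the analysis, so that it is not chosen after the data are seen.

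The cost is a few sentences and a forward shift of test dates when the follow-up intervals are built. No new data are needed. There are real downsides. A true effect acting within the lag is missed by the lagged model, although the unlagged contrast keeps it visible. Early follow-up depends on pre-entry values. A carry-forward limit loses person-time, possibly more among controls if they are tested less often.
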